Robinson ¹⁴ (1 mg/kg q24h; n = 19)	0.40	-	-	-	-

Study Justification

Ideal enoxaparin dose for VTE prevention in high-risk trauma patients is unknown. Predictors and explanations for low anti-Xa are also unknown. With emerging evidence demonstrating around 50% of trough anti-Xa concentrations are subtherapeutic and associated with increased VTE risk, the purpose of this study is to compare AT-III serum concentrations as a predictor of low anti-Xa. Secondly, the study will compare two enoxaparin dosing. Ultimately, this information can be used to develop an optimum protocol for patient-specific enoxaparin dosing for VTE prevention to improve patient outcomes.

METHODS**Study design**

This is an investigator-initiated, single-center, prospective, non-blinded, randomized controlled trial. Multi-system trauma patients between 18-80 years old admitted to the University of Cincinnati Medical Center (UCMC), an urban American College of Surgeons-verified Level 1 trauma center will be identified by the Trauma Surgery team. The trauma team will inform study personnel of these patients once enoxaparin is initiated. These patients will be screened for inclusion in the study. Patients who meet inclusion criteria will be administered informed consent by study personnel in their rooms. Patients in the surgical intensive care unit (SICU) and on the surgical floor are eligible for enrollment if all other inclusion and exclusion criteria are met. Informed consent will be obtained prior to enrollment. Goal enrollment is 200 patients with 100 patients in the control group and 50 patients in each randomization group.

Research data collection/study procedures

Patients will be screened daily by the trauma team. Research personnel will be alerted to potential patients for enrollment.

Intervention

Serum AT-III and anti-Xa will be drawn eight hours after the third dose of enoxaparin 30 mg q12h. Serum assays after at least the third dose should approximate drug steady state trough concentrations. Patients with a serum anti-Xa ≥ 0.1 IU/mL will remain on enoxaparin 30 mg every 12 hours and will be the control group. Patients with undetectable anti-Xa (intervention groups), defined as a trough anti-Xa < 0.1 IU/mL, will be randomized to receive either:

- a. Enoxaparin 40 mg every 12 hours (group 1)
- b. Enoxaparin 30 mg every eight hours (group 2)

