Subsequent trough anti-Xa levels will be performed eight hours after the third dose. Repeat anti-Xa levels will be drawn eight hours after the third dose of the new regimen(s) (see attached figures) for patients in the treatment arms and eight hours after the sixth dose for those in the control arm. For patients in group 2, anti-Xa levels will be drawn within 30 minutes of the fourth and eighth doses. If patients continue to be subtherapeutic, the group 1 dose will be increased to 50 mg every 12 hours, while the group 2 dose will remain at 30 mg every eight hours. Group 2 will not have subsequent dose adjustment, as this regimen has not been previously evaluated. Coordinated AT-III and TEG will be performed with the first anti-Xa assessment and the first repeat assessment in the interventional groups. After the initial assessments, weekly anti-Xa and AT-III will be collected on patients requiring dose adjustment for up to 28 days. If the weekly trough anti-Xa level is ≥ 0.3 IU/mL, the enoxaparin dose will be decreased to the previous dose (i.e., enoxaparin 50 mg every 12 hours would be decreased to 40 mg every 12 hours; enoxaparin 40 mg every 12 hours would be decreased to 30 mg every 12 hours; enoxaparin 30 mg every eight hours would be decreased to 30 mg every 12 hours) with patient remaining in enrolled study group for all outcome analyses.

Randomization

Following informed consent, serum AT-III and anti-Xa values will be assayed per protocol. Patients with an anti-Xa level < 0.1 IU/mL undergo unblinded 1:1 randomization to ensure equal allocation to each intervention group. Randomization will be performed by study personnel. If the standard of care anti-Xa per trauma protocol is not collected or inappropriately drawn/mistimed by nursing or phlebotomy staff, patients will be able to have a repeat standard of care anti-Xa within 24 hours of initial draw for assignment to treatment or control groups for enrollment and outcome analysis (protocol amendment). This practice aligns with the current daily trauma protocol operations.

Data Collection:

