Coordinated serum anti-Xa, AT-III, and TEG will be collected as previously described. Time to goal anti-Xa achievement will be collected as previously described. Additional data to be collected include patient sex, age, weight, body mass index (BMI), body surface area (BSA), injury mechanism (blunt vs. penetrating), ISS, abbreviated injury score ([AIS] for head, chest, abdomen, extremity, cervical spine, thoracic spine, and lumbar spine), RAP, admission and highest serum creatinine, admission and lowest creatinine clearance (Cockcroft and Gault calculated), admission unit (e.g., ICU; floor), time to enoxaparin initiation, heparin initiation (days and number of doses) prior to enoxaparin therapy, VTE events specified, length of stay (hospital and ICU), 28-day mortality, major and minor bleeding events, overall mortality, interruption of study drug, cumulative fluid balance from admission with each serum assay, total milliliters of transfused fluid to date at each anti-Xa assessment, and milliliters of packed red cells transfused in specified time frame.

Specimen collection

Serum assays will be collected as previous described. In summary, initial AT-III and anti-Xa concentrations will be performed eight hours after the third dose of enoxaparin 30 mg q12h. Repeat anti-Xa assessment will be performed after the third dose of the new enoxaparin regimen, based on patient randomization. Coordinated AT-III and TEG will be performed with the first anti-Xa assessment and the first repeat assessment in the interventional group. After the initial assessments, weekly anti-Xa and AT-III will be collected on patients requiring dose adjustment for up to 28 days. All serum anti-Xa and coordinated AT-III and TEG will be drawn 30 minutes prior to stated dose.

Subjects will have the serum assays drawn by either nursing staff via central catheter access or phlebotomy via peripheral venous access. All labs will be drawn using two 2.7 mL blue top, sodium citrate tubes. One tube is needed for the TEG, while the other is used for the AT-III and anti-Xa.

Potential Benefits

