2. Proportion of patients reaching goal anti-Xa between group 1 and group 2 overall, at first repeat assessment, and at second repeat assessment.
3. Median time to achievement of goal anti-Xa between group 1 and group 2.

Secondary Endpoints

1. Patient outcomes to be compared between control and intervention groups including all VTE events (i.e., pulmonary embolism; upper extremity deep venous thromboembolism [DVT]; proximal lower extremity DVT; distal lower extremity DVT), major bleeding (i.e., hemoglobin decrease of ≥ 2 g/dL in a 24 hour period requiring ≥ 2 units of packed red blood cells while on enoxaparin; worsened or new intracranial hemorrhage while on enoxaparin; repeat surgical intervention due to hemorrhage while on enoxaparin), minor bleeding (minor gastrointestinal bleeding [coffee ground emesis with or without < 2 units packed red cell transfusion needed while on enoxaparin]; interruption of study drug by trauma team; other overt bleeding not characterized a major while on enoxaparin), total transfusion requirements after 48 hours until discharge or admission day 28.
2. Proportion of patients with enoxaparin bioaccumulation (defined as an anti-Xa ≥ 0.3 IU/mL at any assay) between group 1 and 2.
3. Risk factor determination for low anti-Xa.

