- h. Patients with a RAP score ≥ 5 without enoxaparin initiated within 72 hours of admission
- i. Pregnancy
- j. Incarceration

Patients with a 50% change in serum creatinine or an absolute change in serum creatinine by 1 mg/dL after randomization will be removed from the study. If these changes in renal function occur after patient has received initial laboratory assessment (i.e., anti-Xa; AT-III; TEG), the patient will be included in the primary outcome analysis per intention-to-treat design.

Consenting process and plan

Patients will be identified as previously described per trauma service. Permission to consent per the trauma team attending will be obtained prior to administration of consent. Patients initiated on enoxaparin 30 mg every twelve hours prior per the trauma protocol who meet inclusion and exclusion criteria will be eligible for consent. Study personnel will administer in the patient's room. Informed consent will be obtained prior to first serum laboratory assay. The trauma team should alert research personnel as soon as possible for administration of informed consent. Patients will be able to be consented and enrolled up to four hours prior to the first serum laboratory assay. At-risk or vulnerable patients unable to give consent will have next of kin consented. Investigators will be available seven days a week and will

continue correspondence with subjects throughout the study and until hospital discharge (see “Informed Consent” form).

Compensation

Patients will not receive any direct compensation for research involvement.

Subject costs

[figure not shown]
There are no additional costs to subjects.

REFERENCES

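### The transfusion endpoint starts at 48 hours with no stated origin; if counted from admission, it can include blood given before group assignment and even before enoxaparin

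*Combined protocol and SAP*

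**What the plan says.** Data Analysis, Secondary Endpoints, item 1 lists transfusion among the outcomes compared between groups: "Patient outcomes to be compared between control and intervention groups including all VTE events", ending with "total transfusion requirements after 48 hours until discharge or admission day 28". The start of that window has no stated origin; its end is tied to the admission calendar. In the same item, major bleeding, gastrointestinal bleeding and other overt bleeding are restricted to time on enoxaparin. The transfusion total has no such restriction.

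The groups form later. Under Intervention, "Serum AT-III and anti-Xa will be drawn eight hours after the third dose of enoxaparin 30 mg q12h", and "Patients with a serum anti-Xa ≥ 0.1 IU/mL will remain on enoxaparin 30 mg every 12 hours and will be the control group". Under Randomization, "Patients with an anti-Xa level < 0.1 IU/mL undergo unblinded 1:1 randomization". If the draw is missed or mistimed, that section allows a repeat within 24 hours. Exclusion criterion h removes "Patients with a RAP score ≥ 5 without enoxaparin initiated within 72 hours of admission", so a first dose as late as hour 72 is eligible.

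Data Collection records "total milliliters of transfused fluid to date at each anti-Xa assessment" and, separately, packed red cells over a period it does not define.

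**The concern.** Blood given before a patient belongs to a group cannot result from that group's regimen. Specific aim 2 uses transfusion to compare the dosing strategies, and the Background takes a similar 48-hour measure in an earlier dalteparin study as evidence of safety, so this result is likely to be read the same way.

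The control and intervention groups are separated by anti-Xa level, not by randomisation. The Background reports edema as associated with low anti-Xa, and aim 3 treats cumulative fluid as a possible correlate. Heavily resuscitated patients could therefore be unevenly spread between the two groups. Late starters may also have had more early bleeding, since ongoing hemorrhage and uncorrected coagulopathy are listed as contraindications to starting prophylaxis. The planned comparison of continuous outcomes is an unadjusted t-test or rank-sum test, which would not remove an imbalance in earlier transfusion.

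**Working it through.** The plan gives no numerical figure for this endpoint, and Table 2 has no transfusion row. There is no stated figure to reproduce, and the sample size is not affected. The check is clock arithmetic.

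**Inputs**
- T = hours from admission to first enoxaparin dose, 0 to 72 (Exclusion Criteria, h).
- Doses every 12 hours, so the third dose is at T + 24 (Intervention).
- Grouping assay 8 hours after the third dose (Intervention).
- Redraw up to 24 hours later (Randomization).
- Window opens at hour 48 from admission (assumed) and closes at discharge or day 28, which is 28 × 24 = 672 hours.

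**Time of assignment**
- Assay at T + 24 + 8 = T + 32, which ranges from 32 to 104 hours after admission.
- With the latest redraw, T + 56, so up to 128 hours.

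**Pre-assignment hours inside the window** = max(0, T + 32 − 48) = max(0, T − 16). **Hours before any enoxaparin** = max(0, T − 48).

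| First dose (T) | Assay | Pre-assignment hours counted | With latest redraw | Hours before any enoxaparin |
|---|---|---|---|---|
| 12 | 44 | 0 | 20 | 0 |
| 16 | 48 | 0 | 24 | 0 |
| 24 | 56 | 8 | 32 | 0 |
| 48 | 80 | 32 | 56 | 0 |
| 72 | 104 | 56 | 80 | 24 |

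**Share of the window.** For a stay to day 28 the window is 672 − 48 = 624 hours. At T = 72 the pre-assignment part is 56/624 = 9%, or 80/624 = 13% with the latest redraw. Earlier discharge makes the share larger.

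**Other origins**
- First enoxaparin dose: the assay at 32 hours comes before hour 48, so there is no overlap without a redraw. With the latest redraw it is 56 − 48 = 8 hours. No time before enoxaparin is counted, but without a redraw the first 48 − 32 = 16 hours after the assay are left out.
- Randomisation: no overlap, but the first 48 hours on the new regimen are left out, and controls, who are not randomised, have no origin.

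**Assay timing.** Specimen collection also says that draws are made 30 minutes before a dose. For 12-hourly dosing that puts the first assay at T + 36 − 0.5 = T + 35.5 and moves the threshold from hour 16 to 48 − 35.5 = hour 12.5. The two statements need reconciling; the conclusion is the same under either.

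**The case against.** The strongest objection is that the admission origin is inferred. The endpoint does not state it, and neither does the Background's account of the dalteparin study. From the first dose the overlap nearly disappears; from randomisation it does disappear. This stands: the demonstrable defect is an undefined origin, and the overlap follows only on the natural reading. Neither alternative, however, starts the count at assignment for everyone.

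A reader might infer that the comparison necessarily includes blood given before the assigned regimen. The documents do not support that. Patients who start by about hour 16 and need no redraw contribute no pre-assignment time. Controls stay on the dose they were already receiving, so for them the issue is blood given before classification or before any enoxaparin, not before a change of regimen.

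A reader might also infer a bias against the intervention groups. That too is unsupported. The documents give no distribution of start times and no transfusion rates, so the figures above are hours, not volumes, and the direction is unknown. Between groups 1 and 2, randomisation balances earlier transfusion on average.

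A 48-hour cut-off may be meant to leave out initial resuscitation, which is a reasonable aim. Starting at assignment meets that aim at least as well for late starters. Finally, this is one component of a secondary endpoint in a pilot study, alongside bleeding criteria mostly limited to time on the drug. That limits the severity but does not answer the point.

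**Conclusion.** The point holds in a conditional form. The origin of the 48 hours is not stated. If it is admission, the transfusion total can include time before assignment for starts after about hour 16, reaching 56 hours at the latest permitted start (80 with the latest redraw), and up to 24 hours before any enoxaparin for starts after hour 48. Nothing else in the plan removes that time. The likely effect is noise in group 1 versus group 2 and possible bias, of unknown size and direction, in control versus intervention. The conclusion rests on the admission origin, on-schedule 12-hourly dosing, and assignment at the assay; any wait for the result would lengthen the overlap.

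**What to change.** Define the endpoint as volume transfused from group assignment, taken as the first-assay result used for assignment (including a redraw), to discharge or admission day 28, in all three groups. Use the same window for the undefined packed-red-cell period in Data Collection.

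If the volume is derived by subtraction, subtract the running total at that assay from a cumulative total since admission for the same product type. Do not subtract it from the after-48-hour total, because that removes blood never counted. As an illustration, take 2,000 mL before hour 48, none until the assay and 300 mL afterwards. The correct figure is 2,300 − 2,000 = 300 mL; the mismatched subtraction gives 300 − 2,000 = −1,700 mL.

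Keep the after-48-hour total, with its origin stated, as a descriptive figure.

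The cost is small: a revised endpoint definition, a matching line in Data Collection and, if subtraction is used, a closing cumulative volume, which Data Collection does not list. Sample size and patient care are unchanged. The downside is slightly less comparability with the earlier dalteparin study's 48-hour measure, which the descriptive figure largely preserves.

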Venous thromboembolism (VTE) is a common, potentially life-threatening complication in high-risk trauma patients. With emerging evidence demonstrating around 50% of trough serum anti-factor Xa (anti-Xa) concentrations are subtherapeutic and associated with increased VTE risk, the purpose of this pilot study is to evaluate the safety and efficacy of a novel enoxaparin dosing strategy based on anti-Xa values. High-risk patients (e.g., risk assessment profile score ≥ 5) initiated on enoxaparin 30 mg q12h per current trauma team standard of care. Patients will be excluded for renal dysfunction (Cockcroft-Gault calculated creatinine clearance < 30 mL/min or patients on continuous renal replacement therapy), weight < 50 kg or > 150 kg, nephrotic syndrome, platelet count $< 50 \times 10^3$, allergy to heparin, patients on or requiring therapeutic anticoagulation at or within 24 hours of admission, isolated intracranial hemorrhage, known hyperbilirubinemia, pregnancy, or incarceration. Primary outcome is the comparison of antithrombin-III (AT-III), proportion of anti-Xa goal achievement at first, second, and all assessments, and time to goal anti-Xa. Patient outcomes include VTE events, bleeding outcomes, patients with bioaccumulation, and risk factors for low anti-Xa.

Purpose of Study

The purpose of this pilot study is to compare two enoxaparin dosing strategies: BID dosing and a dosing strategy based on anti-Xa values in high-risk trauma patients. Specific aims include: 1) to compare the extent of reduced AT-III activity between patients with anti-Xa ≥ 0.1 IU/mL and < 0.1 IU/mL upon initial assay and determine the proportion of patients who reach goal anti-Xa and time to goal anti-Xa between two dosing strategies: enoxaparin 40 mg every 12 hours (with consideration to increase to 50 mg every 12 hours if recheck anti-Xa is not at goal; see section 6) and enoxaparin 30 mg every eight hours; 2) to compare anti-Xa adjusted enoxaparin-dosing strategies based on VTE, bleeding rates, transfusion requirements, drug discontinuation rate and bioaccumulation, and 3) to determine patient-specific factors that correlate to subtherapeutic anti-Xa such as serial AT-III activity, weight, body mass index, age, cumulative fluid administration and thromboelastography (TEG).

Background

Background and Significance

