Statistical analyses will be performed using SAS version 9.3 (SAS Institute, Inc., Cary, NC). An intention-to-treat model will be used for data analysis. Patients excluded due to change in renal function will be included in the primary outcome analysis, but not patient outcome analyses for VTE and bleeding outcomes. Nominal data will be reported using frequencies of occurrence and proportions as appropriate. Continuous data will be reported using means and standard deviations or medians and ranged as appropriate per distribution. Hypothesis testing for nominal data will be performed using the Fisher's exact test or chi square test as required based on sample size. Continuous data will be compared using student's t-test/ANOVA or rank sum/Kruskal-Wallis ANOVA for normally distributed and non-normally distributed data, respectively. A p-value < 0.05 will designate statistical significance. Time-to-event analyses will be compared as appropriate and presented as Kaplan-Meier curves. Multivariate logistic regression will be performed for low anti-Xa risk determination. All values with a p-value < 0.2 will be included in the model. Serum AT-III, weight, and age will be forced into the model, regardless of p-value.

A total of 200 patients will be enrolled. Assuming that 50% of patients will have an undetectable anti-Xa on enoxaparin 30 mg every 12 hours, we hypothesize the intervention group will have an absolute reduction in AT-III activity of 10% compared to the control group if the control group has a mean AT-III activity of 80% with a standard deviation of 25%. Secondly, we hypothesize that there will be an absolute difference of 27% in the proportion of patients who achieve goal anti-Xa between group 1 and group 2, assuming 50% of group 1 achieves goal. To achieve an 80% power with an alpha of 0.05 for both outcomes, goal enrollment is 200 patients (table 2).

Table 2. Power analysis for each outcome

AT-III activity difference between control and intervention			
Absolute difference in means	Standard Deviation		Sample Size
10%	25%		200
10%	30%		286
10%	10%		34
20%	30%		74
20%	10%		12
Anti-Xa ≥ 0.1 IU/mL attainment between group 1 and group 2			
Group 1 Proportion	Group 2 Proportion		Sample Size
50%	77%		100
50%	75%		116
60%	80%		164
80%	90%		398
70%	80%		588
VTE reduction between study groups			
Estimate Source	Control Proportion	Intervention Proportion	Sample Size
Malinoski ¹⁵	37%	11%	98

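### Intention-to-treat is declared, yet patients with a creatinine change after group assignment are left out of the VTE and bleeding analyses, so events before their removal are lost

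*Combined protocol and SAP*

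**What the plan says.** The statistical methods paragraph under Data Analysis states: "An intention-to-treat model will be used for data analysis". The next sentence says that patients taken out "due to change in renal function will be included in the primary outcome analysis, but not patient outcome analyses for VTE and bleeding outcomes".

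The rule behind these exclusions closes the Exclusion Criteria: anyone who has "a 50% change in serum creatinine or an absolute change in serum creatinine by 1 mg/dL after randomization will be removed from the study". Where the initial assays were already done, "the patient will be included in the primary outcome analysis per intention-to-treat design". Level of Risk gives the same rule without tying it to randomisation.

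The outcomes concerned are in Secondary Endpoints, item 1: "Patient outcomes to be compared between control and intervention groups including all VTE events". Bleeding is counted only on drug, for example "worsened or new intracranial hemorrhage while on enoxaparin". Aim 2 under Purpose of Study is "to compare anti-Xa adjusted enoxaparin-dosing strategies based on VTE, bleeding rates, transfusion requirements, drug discontinuation rate and bioaccumulation". The opening summary says that "the purpose of this pilot study is to evaluate the safety and efficacy of a novel enoxaparin dosing strategy", so safety is a stated purpose.

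**The concern.** Removal depends on something that happens after group assignment, and it takes out the whole patient, not only the time after removal. Suppose a patient has a qualifying bleed on enoxaparin on day 5 and the creatinine limit is crossed on day 8. Under the rule as written, that bleed is not counted.

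The trigger is also not neutral with respect to the outcome. Pharmacokinetic / Safety Information justifies the renal exclusion at entry by the bleeding risk that comes with slower drug elimination, and Level of Risk names bleeding as the hazard of the higher doses. If removals differ between groups, the groups compared on VTE and bleeding are no longer the groups as assigned.

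**Working it through.** **1. The plan's own figure.** The point rests on no sample-size number. As a check, 2 x (1.96 + 0.8416)² x 25² / 10² = 98.1, so 99 per group and 198 in total, against 200 stated. For 50% versus 77%, the usual two-sided formula without continuity correction gives 49 per group and 98 in total, against 100 stated. Both reproduce, and keeping all patients leaves the goal of 200 unchanged.

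**2. Is the exclusion cured elsewhere?**
- The Intervention section keeps a patient in the enrolled group for every outcome analysis after a dose step-down. That sentence covers step-downs for a trough of 0.3 IU/mL or more, not renal removals.
- The Exclusion Criteria invoke intention-to-treat for the primary outcome only.
- No sentence counts events before removal, and no sensitivity analysis restores these patients.

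**3. Which comparisons are touched?**
- Control versus intervention on VTE and bleeding: yes, as listed in Secondary Endpoints, item 1. Controls are selected by an anti-Xa of at least 0.1 IU/mL, so this comparison is not randomised.
- Group 1 versus group 2 on VTE and bleeding: yes, but through Aim 2 and the unrestricted wording of the exclusion, not through the endpoint list.
- Bioaccumulation (Secondary Endpoints, item 2, group 1 versus group 2) and the primary endpoints: not excluded.

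**4. Expected VTE.** Expected count = group size x Table 2 rate, with the control column applied to 100 controls and the intervention column to a randomised group of 50. The share of one event is 1 / expected count.

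| Table 2 row | 100 controls | One event | Group of 50 | One event |
|---|---|---|---|---|
| Registry, 5.5% v 2.5% | 5.5 | 18% | 1.25 | 80% |
| Registry, 5.5% v 4.5% | 5.5 | 18% | 2.25 | 44% |
| Dalteparin protocol study, 14.5% v 5.5% | 14.5 | 7% | 2.75 | 36% |
| Enoxaparin trough study, 37% v 11% | 37 | 3% | 5.5 | 18% |

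These shares apply only if a removed patient had a VTE. They show how thin the counts are; they do not estimate the bias.

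**5. Bleeding, under assumptions.** The documents give no bleeding rate. As an illustration, take 3/50 = 6.0%. Dropping one patient who bled gives 2/49 = 4.1%; dropping one who did not gives 3/49 = 6.1%.

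Let f be the fraction removed and k their bleeding risk relative to the rest (both assumed). With p the risk in the rest, the true rate is p[1 + f(k - 1)] and the reported rate is p, so reported/true = 1/[1 + f(k - 1)].
- f = 5%: k = 0.5 gives 1/0.975 = 1.03; k = 3 gives 1/1.10 = 0.91.
- f = 10%: k = 0.5 gives 1/0.95 = 1.05; k = 3 gives 1/1.20 = 0.83.
- k = 1 gives 1.00 for any f.

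A true 6.0% would be reported as 5.0% to 6.3%.

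**6. Unequal removal, a deliberately adverse illustration.** Assume 5% removed in one group and 10% in the other, with a risk of 20% in removed patients and 3% in the rest. True rates are 0.05 x 20% + 0.95 x 3% = 3.85% and 0.10 x 20% + 0.90 x 3% = 4.70%, a difference of 0.85 points. After the exclusion both read 3.0%. Here k = 20/3 = 6.7, which has no source in the documents.

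**7. A trap in the obvious repair.** Secondary Endpoints, item 1 counts a trauma-team interruption of study drug as minor bleeding. If renal patients are retained and their dosing is stopped, each could be coded as a bleed. At 5% to 10% of 50 that is 2.5 to 5 false events. Added to the illustrative 3, this gives 5.5/50 = 11% to 8/50 = 16%, a larger distortion than the one being repaired.

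**The case against.** The exclusion is stated openly, directly after the intention-to-treat sentence, so the set is in effect a modified intention-to-treat set for secondary outcomes. The study is a pilot and VTE is not a powered outcome: Table 2's registry rows need 1468 patients or more. A medical monitor reviews all adverse events, so safety oversight during the trial does not depend on this analysis set. Stopping study dosing when renal function worsens is sound. Over the assumed range in step 5, the illustrative bleeding rate moves by at most about one percentage point, or half a patient in 50.

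These points limit the severity. They do not justify the rule: stopping a drug does not require dropping the patient from the analysis, and disclosure does not make the analysis intention-to-treat.

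Three stronger readings are tempting and are not supported:
- *Bleeding is understated.* That holds only if removed patients bleed more than the rest. With equal risk the rate is unchanged, and with lower risk it is slightly overstated.
- *The only randomised safety comparison is broken.* Bioaccumulation is also compared between group 1 and group 2 and is not excluded. The endpoint list gives VTE and bleeding as control versus intervention, where there is no randomisation to protect.
- *The main results are compromised.* The primary endpoints keep these patients.

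**Conclusion.** The concern holds in a limited form. The plan names intention-to-treat but discards VTE and bleeding events in patients who later meet the creatinine rule, including bleeds on enoxaparin before removal. This affects the listed non-randomised comparison and, by way of Aim 2, the randomised comparison of the two regimens on these outcomes.

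The reading of the text is firm; the size is not. No removal rate, bleeding rate or relative risk is given, so the ratio of 0.83 to 1.05 rests entirely on the assumed f and k. What the documents do support is that counts are small: 5.5 expected VTE in 100 controls and 1.25 to 2.25 in a group of 50 at the registry rates. Severity is modest, since these are secondary outcomes in a pilot, but the change is worth making because safety is a stated purpose and the repair is cheap.

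**What to change.** Make three linked changes.

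- **Data Analysis.** Replace the exclusion with: *Patients who meet the renal rule stay in all outcome analyses, including VTE and bleeding, in their assigned group. A sensitivity analysis leaves them out. The number meeting the rule and the days on enoxaparin are reported by group.*
- **Level of Risk and the close of Exclusion Criteria.** Replace removal with: *Study dosing stops, the trauma team sets further prophylaxis, and outcome follow-up continues.*
- **Secondary Endpoints, item 1.** Limit the minor-bleeding item on interruption of study drug to interruptions made because of bleeding, so that a renal stop is not counted as a bleed. The first two changes should not be made without this one.

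The cost is wording in four places and continued recording of VTE and bleeding after the rule is met. Data Collection already lists VTE, major and minor bleeding, and drug interruption. The downside is that part of these patients' follow-up is off the assigned dose and their on-drug bleeding window is shorter, which is why days on enoxaparin should be reported next to the bleeding proportions.
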